Association between the Quantitative Assessment of Schistocytes in Peripheral Blood Smear and Prognosis of Patient Initially Diagnosed as HELLP Syndrome

Thesis

Submitted for partial fulfillment of Master Degree in
Obstetrics & Gynecology

Presented by
[name]

M. B., B. Ch.2009

Faculty of Medicine, Ain Shams University
Work at Abu Sewair medical administration

Under the supervision of
Ass. [name] [name]

Assistant Professor of Obstetrics and Gynecology
Faculty of Medicine, Ain Shams University

Lecturer. [name]

Lecturer of Obstetrics and Gynecology
Faculty of Medicine, Ain Shams University

Lecturer. [name]

Lecturer of Clinical and Chemical Pathology
Faculty of Medicine, Ain Shams University

Faculty of Medicine
Ain Shams University

2016

*Association between the Quantitative Assessment of Schistocytes in Peripheral Blood Smear and
Prognosis of Patient Initially Diagnosed as HELLP Syndrome (Study results)*

Results

The current study was conducted at Ain Shams University Maternity Hospital during the period between January 2015 and December 2015. A total of 100 women with an initial diagnosis of HELLP syndrome were recruited in the study. Blood sample taken within 12hrs peripartum and patients followed up 48hrs after delivery and subdivided in to 2 groups according to improvement or deterioration after 48hrs after delivery . All results were collected, tabulated and statistically analyzed.

Table-4 and figures 8-10 show the initial characteristics of included women.

Table-4 Initial Characteristics of Included Women .

Age (years)	
Range	18 – 38
Mean ± SD	27.51 ± 4.98
Parity	
Range	0 – 5
Median (IQR)	1 (1 – 2)
Gestational Age (weeks)	
Range	27 – 38
Mean ± SD	34.3 ± 2.91

SD standard deviation

IQR interquartile range [central 50% of ascendingly-ordered set of data]

Data presented as range, mean \pm SD; or range, median (IQR)

Figure-8 Bar-Chart showing Maternal Age Distribution in Included Women .

[figure not shown]

Figure-9 Pie-Chart showing Parity Distribution in Included Women .

[figure not shown]

Figure-10 Bar-Chart showing Gestational Age Distribution in Included Women .

[figure not shown]

Table-5 and figures 11-18 show the initial clinical and laboratory data of included women.

Table-5 Initial Clinical and Laboratory Data in Included Women .

Initial Data	
Systolic Blood Pressure (mm Hg)	
Range	170 – 240
Median (IQR)	180 (170 – 190)
Diastolic Blood Pressure (mm Hg)	
Range	90 – 150
Median (IQR)	100 (100 – 120)
Albuminuria	
3+	41 (41%)
4+	32 (32%)
5+	27 (27%)
Hb Concentration (g/dl)	
Range	6.5 – 9.8
Median (IQR)	8.7 (8 – 9)
Platelet Count (x 10,000 per mm³)	
Range	28 – 97
Median (IQR)	77 (67 – 85)
Serum ALT (u/l)	
Range	91 – 895
Median (IQR)	200 (149 – 278)
Serum AST (u/l)	
Range	79 – 779
Median (IQR)	179 (135 – 250)
Serum Total Bilirubin (mg/dl)	
Range	1.2 – 7.9
Median (IQR)	2.3 (1.6 – 3.3)
Serum Creatinine (mg/dl)	
Range	1.4 – 6.3
Median (IQR)	1.9 (1.8 – 2.1)

IQR interquartile range [central 50% of ascendingly-ordered set of data]

Data presented as range, median (IQR); or number (percentage)

Hb hemoglobin

ALT alanine transaminase

AST aspartate transaminase

Figure-11 Box-Plot Chart showing Initial Systolic and Diastolic Blood Pressure in Included Women .

[figure not shown]

Figure-12 Pie-Chart showing Albuminuria in Included Women .

[figure not shown]

Figure-13 Box-Plot Chart showing Initial Hb Concentration in Included Women .

[figure not shown]

Figure-14 Box-Plot Chart showing Initial Platelet Count in Included Women .

[figure not shown]
[figure not shown]

Figure-15 Box-Plot Chart showing Initial Liver

Transaminases in Included Women .

Figure-16 Box-Plot Chart showing Initial Serum Bilirubin and Creatinine in Included Women .

[figure not shown]

Table-6 and figures 17-21 show the clinical and laboratory data 48 hours postpartum in included women.

Table-6 Clinical and Laboratory Data 48 hours Postpartum in Included Women .

Data 48 hours Postpartum	
Systolic Blood Pressure (mm Hg)	110 – 230
Range	135 (120 – 185)
Median (IQR)	
Diastolic Blood Pressure (mm Hg)	60 – 130
Range	90 (70 – 100)
Median (IQR)	
Hb Concentration (g/dl)	5 – 13.3
Range	9.7 (7.12 – 11)
Median (IQR)	
Platelet Count (x 10,000 per mm³)	20 – 303
Range	115 (65 – 135)
Median (IQR)	
Serum ALT (u/l)	7 – 2165
Range	55 (25 – 281.5)
Median (IQR)	
Serum AST (u/l)	7 – 2143
Range	36 (15 – 250)
Median (IQR)	
Serum Total Bilirubin (mg/dl)	0.1 – 10
Range	1.3 (1.1 – 1.8)
Median (IQR)	
Serum Creatinine (mg/dl)	0.5 – 14.5
Range	0.75 (0.6 – 2.75)
Median (IQR)	

IQR interquartile range [central 50% of ascendingly-ordered set of data]

[figure not shown]
[figure not shown]
Data presented as range, median (IQR)

Hb hemoglobin

ALT alanine transaminase

AST aspartate transaminase

[figure not shown]
Figure-17 Box-Plot Chart showing Systolic and Diastolic

Blood Pressure 48 hours Postpartum in Included Women.

Figure-18 Box-Plot Chart showing Hb Concentration 48 hours Postpartum in Included Women .

Figure-19 Box-Plot Chart showing Platelet Count 48 hours

Postpartum in Included Women .

Figure-20 Box-Plot Chart showing Liver Transaminases 48 hours Postpartum in Included Women .

Association between the Quantitative Assessment of Schistocytes in Peripheral Blood Smear and Prognosis of Patient Initially Diagnosed as HELLP Syndrome (Study results)

[figure not shown]
[figure not shown]

Figure-21 Box-Plot Chart showing Serum Bilirubin and

Creatinine 48 hours Postpartum in Included Women .

Of the included 100 women, 25 (25%) women showed clinical and laboratory deterioration 48 hours postpartum. All women who deteriorated postpartum received plasma exchange. Of the included 100 women, 3 (3%) died (table-7, figures 22-23).

Table-7 Postpartum Deterioration and Mortality in Included Women .

Postpartum Deterioration	
Yes	25 (25%)
No	75 (75%)
Received Plasma Exchange-steroids	
Yes	25 (25%)
No	75 (75%)
Maternal Mortality	
Yes	3 (3%)

No	97 (100%)
----	-----------

Data presented as number (percentage)

Figure-22 Pie-Chart showing Postpartum Deterioration in Included Women .

[figure not shown]
[figure not shown]

Figure-23 Pie-Chart showing Maternal Mortality in Included Wome .

There were no significant differences between women who deteriorated postpartum and women who did not regarding age, parity or gestational age (table-8, figures 24-26).

Table-8 Difference between Women who Deteriorated Postpartum and Women who did not regarding Initial Characteristics .

	Women who Deteriorated Postpartum (n=25)	Women who Did not Deteriorate Postpartum (n=75)	P
Age (years)			
Range	18 – 35	18 – 38	0.621*
Mean \pm SD	27.08 \pm 4.58	27.65 \pm 5.13	NS
Parity			
Range	1 – 4	0 – 5	0.972**
Median (IQR)	1 (1 – 2)	1 (1 – 2)	NS
Gestational Age (weeks)			
Range	27 – 38	27 – 38	0.407*
Mean \pm SD	33.88 \pm 3.14	34.44 \pm 2.83	NS

SD standard deviation

IQR interquartile range [central 50% of ascendingly-ordered set of data]

[figure not shown]
Data presented as range, mean \pm SD; or range, median (IQR)

* Analysis using Independent Student's t-test

** Analysis using Mann-Whitney's U-Test

NS non-significant

Figure-24 Box-Plot Chart showing Difference between Women who Deteriorated Postpartum and Women who did

not regarding Maternal Age .

Figure-25 Box-Plot Chart showing Difference between Women who Deteriorated Postpartum and Women who did not regarding Parity .

Association between the Quantitative Assessment of Schistocytes in Peripheral Blood Smear and Prognosis of Patient Initially Diagnosed as HELLP Syndrome (Study results)

[figure not shown]
[figure not shown]

Figure-26 Box-Plot Chart showing Difference between Women who Deteriorated Postpartum and Women who did

not regarding Gestational Age .

There were no significant differences between women who deteriorated postpartum and women who did not regarding the initial values of systolic blood pressure, diastolic blood pressure, albuminuria, hemoglobin concentration, platelet count or serum creatinine. The initial levels of serum ALT, AST and total bilirubin were, however, significantly, higher in women who deteriorated postpartum (table-9, figures 27-34).

Table-9 Difference between Women who Deteriorated Postpartum and Women who did not regarding Initial Clinical and Laboratory Data .

Initial Data	Women who Deteriorated Postpartum (n=25)	Women who Did not Deteriorate Postpartum (n=75)	P
Systolic Blood Pressure (mm Hg) Range	170 – 190	170 – 240	0.366*

Association between the Quantitative Assessment of Schistocytes in Peripheral Blood Smear and Prognosis of Patient Initially Diagnosed as HELLP Syndrome (Study results)

Median (IQR)	180 (170 – 190)	180 (170 – 190)	NS
Diastolic Blood Pressure (mm Hg)			
Range	100 – 130	90 – 150	0.123*
Median (IQR)	100 (100 – 110)	110 (100 – 120)	NS
Albuminuria			
3+	13 (52%)	28 (37.7%)	
4+	5 (20%)	27 (36%)	0.287**
5+	7 (28%)	20 (26.7%)	NS
Hb Concentration (g/dl)			
Range	6.6 – 9.5	6.5 – 9.8	0.747*
Median (IQR)	8.6 (7.5 – 9.05)	8.7 (8 – 9)	NS
Platelet Count (x 10,000 per mm³)			
Range	41 – 90	28 – 97	0.285*
Median (IQR)	70 (58 – 85)	78 (67 – 85)	NS
Serum ALT (u/l)			
Range	91 – 895	95 – 494	0.043*
Median (IQR)	287 (145 – 448)	196 (155 – 233)	S
Serum AST (u/l)			
Range	87 – 779	79 – 515	0.004*
Median (IQR)	256 (155 – 430)	170 (125 – 224)	S
Serum Total Bilirubin (mg/dl)			
Range	1.4 – 7.9	1.2 – 5.2	<0.001*
Median (IQR)	3.4 (2.4 – 4.2)	1.9 (1.6 – 2.7)	HS
Serum Creatinine (mg/dl)			
Range	1.5 – 6.3	1.4 – 3.8	0.105*
Median (IQR)	2 (1.8 – 2.3)	1.9 (1.8 – 2)	NS

IQR interquartile range [central 50% of ascendingly-ordered set of data]

[figure not shown]
Data presented as range, median (IQR); or number (percentage)

* Analysis using Mann-Whitney's U-Test

** Analysis using Chi-squared Test

[figure not shown]
NS non-significant – S significant – HS highly significant

Figure-27 Box-Plot Chart showing Difference between Women who Deteriorated Postpartum and Women who did

not regarding Initial Systolic Blood Pressure .

Figure-28 Box-Plot Chart showing Difference between Women who Deteriorated Postpartum and Women who did

not regarding Initial Diastolic Blood Pressure .

Figure-29 Box-Plot Chart showing Difference between Women who Deteriorated Postpartum and Women who did not regarding Initial Hemoglobin Concentration .

[figure not shown]

Figure-30 Box-Plot Chart showing Difference between Women who Deteriorated Postpartum and Women who did not regarding Initial Platelet Count .

[figure not shown]
[figure not shown]

Figure-31 Box-Plot Chart showing Difference between Women who Deteriorated Postpartum and Women who did

not regarding Initial ALT .

Figure-32 Box-Plot Chart showing Difference between Women who Deteriorated Postpartum and Women who did not regarding Initial AST .

[figure not shown]

Figure-33 Box-Plot Chart showing Difference between Women who Deteriorated Postpartum and Women who did not regarding Initial Serum Total Bilirubin .

Association between the Quantitative Assessment of Schistocytes in Peripheral Blood Smear and Prognosis of Patient Initially Diagnosed as HELLP Syndrome (Study results)

[figure not shown]
[figure not shown]

Figure-34 Box-Plot Chart showing Difference between Women who Deteriorated Postpartum and Women who did

not regarding Initial Serum Creatinine .

The median schistocytes percentage was significantly higher in women who showed postpartum deterioration, when compared to women who did not deteriorate (table-10, figure-35).

Table-10 Difference between Women who Deteriorated Postpartum and Women who did not regarding Schistocytes Percentage .

	Women who Deteriorated Postpartum (n=25)	Women who Did not Deteriorate Postpartum (n=75)	P
Schistocytes (%)			
Range	0 – 44	0 – 6	<0.001*
Median (IQR)	5.5 (2 – 8.4)	0.5 (0.05 – 0.7)	HS

[figure not shown]
IQR interquartile range [central 50% of ascendingly-ordered set of data]

Data presented as range, median (IQR)

* Analysis using Mann-Whitney's U-Test

HS highly significant

Figure-35 Box-Plot Chart showing Difference between Women who Deteriorated Postpartum and Women who did

not regarding Schistocytes Percentage .

The median schistocytes percentage was significantly higher in women who died when compared to women who survived (table-11, figure-36).

Table-11 Difference between Women who Died and Women who Survived regarding Schistocytes Percentage .

	Women who Died (n=3)	Women who Survived (n=97)	P
Schistocytes (%) Range	8.3 – 44	0 – 39	<0.001*
Median (IQR)	39 (8.3 – 44)	0.5 (0.1 – 1.1)	HS

[figure not shown]
IQR interquartile range [central 50% of ascendingly-ordered set of data]

Data presented as range, median (IQR)

* Analysis using Mann-Whitney's U-Test

[figure not shown]
HS highly significant

Figure-36 Box-Plot Chart showing Difference between Women who Died and Women who Survived regarding Schistocytes Percentage .

Receiver operator characteristic (ROC) curve was constructed for schistocytes percentage as a predictor of postpartum deterioration in included women. The curve showed a significant predictability as denoted by the significantly large area under the curve (AUC) (figure-37).

Figure-37 ROC Curve for Schistocytes Percentage as Predictor of Postpartum Deterioration in Included Women .

AUC = 0.883, 95% CI (0.770 to 0.996), $p < 0.001$

Table-15 shows the validity of schistocytes at different cutoff values as predictor of postpartum deterioration.

Table-12 Validity of Schistocytes as Predictor of Postpartum Deterioration in Included Women .

Schistocytes	Sensitivity	Specificity	PPV	NPV	FP	FN	LR+
$\geq 0.95\%$	88%	85.3%	66.7 %	95.5 %	14.7 %	12 %	6
$\geq 1.4\%$	84%	96%	87.5 %	94.7 %	4%	16 %	21
$\geq 1.9\%$	80%	98.7%	95.2 %	93.7 %	1.3%	20 %	60

[figure not shown]
PPV positive predictive value -NPV negative predictive value

FP false positive -FN false negative-LR+ positive likelihood ratio

ROC curves were constructed for initial clinical and laboratory data as predictors of postpartum deterioration. Among all measured variables, only initial ALT, initial AST and initial total bilirubin were significant predictors of postpartum deterioration. Their AUCs, though being significantly large, were smaller than the AUC for

schistocytes; indicating that the latter is a more significant and better predictor for postpartum deterioration (figure-38).

Figure-38 ROC Curves for Initial Clinical and Laboratory Data as Predictors of Postpartum Deterioration in Included Women .

Initial SBP: AUC = 0.441, 95% CI (0.324 to 0.559), p=0.381

Initial DBP: AUC = 0.404, 95% CI (0.283 to 0.525), p=0.152

Initial Hb Concentration: AUC = 0.479, 95% CI (0.341 to 0.616), p=0.750

Initial Platelet Count: AUC = 0.429, 95% CI (0.293 to 0.564), p=0.286

Initial ALT: AUC = 0.636, 95% CI (0.484 to 0.787), p=0.043

Initial AST: AUC = 0.694, 95% CI (0.553 to 0.834), p=0.004

Initial Serum Total Bilirubin: AUC = 0.772, 95% CI (0.656 to 0.887), p=<0.001

Initial Serum Creatinine: AUC = 0.607, 95% CI (0.468 to 0.746), p=0.110

Table-13 shows the validity of initial values of ALT, AST, and total bilirubin as predictors of postpartum deterioration. Again, the validity parameters were remarkably lower than the corresponding parameters of schistocytes.

Table-13 The validity of initial values of ALT, AST, and total bilirubin as predictors of postpartum deterioration.

	Sensitivity	Specificity	PPV	NPV	FP	FN	LR⁺
Initial ALT ≥ 230 u/L	60%	72%	41.7 %	84.4 %	28%	40%	2.1
Initial AST ≥ 240 u/L	60%	84%	55.6 %	86.3 %	16%	40%	3.8
Initial Total Bilirubin ≥ 2.95 mg/dl	68%	81.3%	54.8 %	88.4 %	18.7 %	32%	3.6

ALT alanine transaminase - AST aspartate transaminase

PPV positive predictive value -NPV negative predictive value

[figure not shown]
FP false positive -FN false negative

LR+ positive likelihood ratio

ROC curve was constructed for schistocytes percentage as a predictor of maternal mortality in included women. The curve showed a significant predictability as denoted by the significantly large area under the curve (AUC) (figure-39).

Figure-39 ROC Curve for Schistocytes Percentage as Predictor of Maternal Mortality in Included Women .

Association between the Quantitative Assessment of Schistocytes in Peripheral Blood Smear and Prognosis of Patient Initially Diagnosed as HELLP Syndrome (Study results)

$AUC = 0.985, 95\% CI (0.956 \text{ to } 1.103), p=0.004$

Table-14 shows the validity of schistocytes as predictor of maternal mortality in included women.

Table-14 Validity of Schistocytes as Predictor of Maternal Mortality in Included Women .

Schistocytes	Sensitivity	Specificity	PPV	NPV	FP	FN	LR+
≥ 8.2%	100%	95.9%	42.9%	100%	4.1%	0%	24.3

PPV positive predictive value

NPV negative predictive value

FP false positive

FN false negative

LR+ positive likelihood ratio

There were significant positive correlations between schistocytes percentage and each of systolic and diastolic blood pressures, serum ALT, serum AST, serum total bilirubin and serum creatinine 48 hours postpartum. There were significant negative correlations between schistocytes and each of hemoglobin concentration and platelet count 48 hours postpartum (table-15, figures 40-43).

Table-15 Correlation between Schistocytes and Both Clinical and Laboratory Data 48 hours Postpartum in Included Women .

Data 48 hours Postpartum	Schistocytes		
Systolic Blood Pressure	r_s	0.479	
	P	<0.001	
		HS	
Diastolic Blood Pressure	r_s	0.439	
	P	<0.001	
		HS	
Hb Concentration	r_s	-0.527	
	P	<0.001	
		HS	
Platelet Count	r_s	-0.406	
	P	<0.001	
		HS	

Association between the Quantitative Assessment of Schistocytes in Peripheral Blood Smear and Prognosis of Patient Initially Diagnosed as HELLP Syndrome (Study results)

Serum ALT	r_s	0.373
	P	<0.001 HS
Serum AST	r_s	0.353
	P	<0.001 HS
Serum Total Bilirubin	r_s	0.313
	P	0.002 S
Serum Creatinine	r_s	0.411
	P	<0.001 HS

Hb hemoglobin ,ALT alanine transaminase

AST aspartate transaminase

r_s Spearman's rank correlation coefficient

HS highly significant - S significant

Figure-40 Scatter-Plot Chart showing Correlation between Schistocytes and Platelet Count 48 hours Postpartum in Included Women .

[figure not shown]

Figure-41 Scatter-Plot Chart showing Correlation between Schistocytes and ALT 48 hours Postpartum in Included Women .

Association between the Quantitative Assessment of Schistocytes in Peripheral Blood Smear and Prognosis of Patient Initially Diagnosed as HELLP Syndrome (Study results)

[figure not shown]

Figure-42 Scatter-Plot Chart showing Correlation between Schistocytes and Total Bilirubin 48 hours Postpartum in Included Women .

[figure not shown]

Figure-43 Scatter-Plot Chart showing Correlation between Schistocytes and Serum Creatinine 48 hours Postpartum in Included Women .

Association between the Quantitative Assessment of Schistocytes in Peripheral Blood Smear and Prognosis of Patient Initially Diagnosed as HELLP Syndrome (Study results)

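### The 95% interval for the main AUC (Figure-37, 0.770 to 0.996) is a symmetric normal interval that sits too high and covers about 87-90% rather than 95%

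*SAP*

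**What the plan says.** The protocol (Study Design) describes a pilot study of diagnostic test accuracy. The document supplied as the SAP is a results chapter. It states that "25 (25%) women showed clinical and laboratory deterioration 48 hours postpartum", which leaves 75 who did not.

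Under Figure-37 it gives the main accuracy result: "AUC = 0.883, 95% CI (0.770 to 0.996"), with p<0.001. The sentence above the figure reads: "The curve showed a significant predictability as denoted by the significantly large area under the curve (AUC) (figure-37"). Neither document says how any AUC interval was computed.

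Two tables describe the data behind this AUC. Table-10 gives schistocytes of 0 to 44% (median 5.5, IQR 2 to 8.4) in women who deteriorated and 0 to 6% (median 0.5, IQR 0.05 to 0.7) in those who did not. Table-12 gives sensitivity and specificity of 88% and 85.3% at 0.95%, 84% and 96% at 1.4%, and 80% and 98.7% at 1.9%.

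**The concern.** An AUC near 1 that is estimated from 25 events has a left-skewed sampling distribution. An interval that adds and subtracts the same amount on the raw scale ignores that skew, so it tends to sit too close to 1 and to miss the true value on the low side. The problem is sharper when a few low-ranking women carry most of the variance, as appears to be so here.

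Figure-37 is the study's headline estimate. In a pilot with 25 events, the interval tells a reader as much as the point estimate. If it is shifted upward, both the worst plausible performance and the best are overstated.

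**Working it through.** **Inputs.** AUC 0.883 and limits 0.770 and 0.996 (SAP, Figure-37); 25 and 75 women (SAP, Table-7); schistocyte distributions (Table-10); accuracy at three cut-offs (Table-12). Below, cases are the 25 women who deteriorated and controls the other 75.

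**1. Reproducing the printed interval.** Midpoint (0.770 + 0.996)/2 = 0.883, exactly the AUC. Half-width 0.113. SE = (0.996 − 0.770)/3.92 = 0.0577. The Hanley-McNeil SE for 25 and 75 is 0.0459, giving 0.793 to 0.973, which does not match. A DeLong SE on data rebuilt to fit Tables 10 and 12 with AUC 0.8825 to 0.8835 is 0.058 to 0.061, and the closest fits give 0.769-0.770 to 0.997. The printed interval is thus consistent with AUC ± 1.96 × a nonparametric SE. The mortality AUC (Figure-39) has an upper limit above 1, which also points to limits not held within 0 to 1.

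**2. Where the three lowest cases rank.** Table-12 implies 22, 21 and 20 cases, and 11, 3 and 1 controls, at or above 0.95, 1.4 and 1.9%. A case's placement is the share of controls it outranks, and the placements sum to 25 × AUC.

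- 20 cases at or above 1.9%: 20 × 74/75 = 19.73 to 20.
- One case from 1.4 to below 1.9%: 72/75 to 74/75 = 0.96 to 0.99.
- One case from 0.95 to below 1.4%: 64/75 to 72/75 = 0.85 to 0.96.
- Sum for these 22: 21.55 to 21.95.
- Required total, allowing for rounding of 0.883: 25 × 0.8825 to 25 × 0.8835 = 22.06 to 22.09.
- Left for the other three together: 0.12 to 0.54, a mean placement of 0.04 to 0.18.

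On average these three therefore rank in about the lowest quarter of controls, whose first quartile is 0.05%.

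**3. Intervals that allow for the skew.**

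Logit, from the printed SE: logit(0.883) = 2.021; SE on the logit scale = 0.0577/(0.883 × 0.117) = 0.558; 2.021 ± 1.96 × 0.558, transformed back, gives 0.717 to 0.958.

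The Wilson and Clopper-Pearson rows use an effective sample size of 0.883 × 0.117/0.0577² ≈ 31. The bootstrap rows use the rebuilt data sets that best match both the AUC and the interval.

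| Method | Lower | Upper |
|---|---|---|
| Printed | 0.770 | 0.996 |
| Logit | 0.717 | 0.958 |
| Wilson | 0.726 | 0.955 |
| Clopper-Pearson | 0.717 | 0.970 |
| BCa bootstrap | 0.714-0.724 | 0.961-0.963 |
| Percentile bootstrap | 0.759-0.765 | 0.985-0.987 |

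Leaving out the percentile row, the lower limit falls by 0.044 to 0.056 and the upper by 0.026 to 0.041. The logit width is 0.241 against 0.226, so the printed interval is mainly displaced upward rather than too narrow.

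**4. Coverage.** Drawing 25 cases and 75 controls repeatedly from several separate reconstructions, the symmetric interval covered 87 to 90%. The true AUC lay below its lower limit in 9 to 12% of runs (nominal 2.5%) and above its upper limit in under 1%. The logit interval covered about 92 to 94%, with nearly balanced tails.

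**5. Sensitivity to the assumed share of near-zero cases.** With that share varied from 8 to 20%, the symmetric interval covered 87 to 93%, with 5 to 12% missed on the low side. The logit interval was better at shares of 12% or more and similar or slightly worse below 10%. At 6% both fell to about 78-80%.

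**The case against.** **No conclusion in the documents changes.** This stands. The SAP claims significant predictability and a larger AUC than ALT, AST and bilirubin. Those claims rest on the p-value and the point estimates, and the text never interprets 0.770 or 0.996. A lower limit of about 0.72 is still far above 0.5.

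**The shift depends on the replacement method.** This also stands. A percentile bootstrap lowers the lower limit by only about 0.01, so the 0.04-0.06 belongs to the methods that adjust for skew.

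**The logit interval is not uniformly better.** Correct: with 3 of 25 cases observed (12%), a true share below 10% is well within sampling error, and there it offers no gain.

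**The three low cases are not printed at zero.** Table-10 shows only that at least one case is at 0. The rest is inferred from the placement sum, which would allow one of the three to reach about 0.5% if the other two were at 0.

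A reader might also draw stronger inferences that the documents do not support:

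- *That the corrected lower limit weakens the ranking of schistocytes over bilirubin, because it falls below bilirubin's AUC of 0.772.* The printed 0.770 is already below 0.772. Setting one marker's limit against another's point estimate in the same women is not a paired comparison.
- *That an exact interval for 22 of 25 confirms the result.* That interval concerns sensitivity at 0.95%, a different quantity.
- *That all the intervals in Figure-38 share the fault.* Those AUCs run from 0.404 to 0.772. A logit interval moves their limits by about 0.02 at most; bilirubin goes from 0.656-0.887 to 0.637-0.867.

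**Conclusion.** The point holds in a limited form. The Figure-37 interval is exactly symmetric and miscalibrated. It covers about 87-90% on data consistent with Tables 10 and 12, errs almost wholly on the low side, and sits too high at both ends. Methods that allow for the skew give about 0.72 to 0.96.

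This rests on three assumptions. The method of calculation is inferred from the arithmetic. The coverage figures come from reconstructed data, not the raw values. The advantage of the logit interval requires a true share of near-zero cases of around 10% or more. Exact limits need the raw data. The effect is on stated precision only: it gives no ground for saying that schistocytes fail to discriminate, or that their ranking among the markers is reversed.

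**What to change.** Recompute the Figure-37 interval from the raw data with a logit-transformed DeLong or a BCa bootstrap method, and state the method beside the result. The expected interval is about 0.72 to 0.96. Using the same method in Figure-38 would be for consistency only.

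The cost is one re-run on existing data and a less favourable lower limit. No new data are needed.

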International Council for Standardization in Hematology 2012 (ICSH) has prepared specific recommendations to standardize schistocyte identification, enumeration, and reporting. They deal with the type of smear, method of counting, morphological description based on positive criteria (helmet cells, small, irregular triangular, or crescent-shaped cells, pointed projections, and lack of central pallor). A schistocyte count has a definite clinical value for the diagnosis of TMA in the absence of additional severe red cell shape abnormalities, with a confident threshold value of 1%. Automated counting of RBC fragments is also recommended by the ICSH Working Group as a useful complement to the microscope, according to the high predictive value of negative results, but worthy of further research and with limits in quantitation.

International Council for Standardization in Haematology recommendations for schistocyte counting 2012:

1. Schistocytes should be evaluated on peripheral blood smears using an optical microscope at medium magnification and estimated as a percentage after counting at least 1000 red blood cells.
2. A schistocyte count should be requested and carried out when a diagnosis of thrombotic microangiopathies caused by red cell mechanical damage is suspected, usually in patients with thrombocytopenia.
3. Schistocytes should be identified by specific positive morphological criteria. Schistocytes are always smaller than intact red cells and can have the shape of fragments with sharp angles and straight borders, small crescents, helmet cells, keratocytes, or microspherocytes*.
4. A schistocyte count should be considered clinically meaningful if schistocytes represent the main morphological red blood cells abnormality in the smear (other than signs of erythropoietic regeneration).
5. A robust morphological indication for the diagnosis of thrombotic microangiopathic anemia in adults should be recognized when the percentage of schistocytes is above 1%.
6. Fragmented red cell enumeration by automated blood cell counters should be considered a useful complement to microscopic evaluation, as it provides rapid results with a high predictive value of negative samples. A microscope check is needed for positive and macrocytic samples†.

*Microspherocytes only in the presence of other mentioned RBC shapes.

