†Macrocytic samples are at risk of underestimation or absence of flag ('false negative' test) (***International Council for Standardization in Hematology 2012***).

Schistocytes counting: Schistocytes will be identified and counted on the peripheral blood smear using optical microscopy. The results of microscopic examination then will be expressed as a percentage, after counting at least 1000 RBCs in optimal areas of the film. Interpretation of the examination results had been done following the (***International Council for Standardization in Hematology, 2012***) recommendations for identification, diagnostic value, and quantitation of schistocytes.

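### Tables 12-14 print accuracy at cut-offs without intervals, leave the origin of the cut-offs unstated, and claim a lead for schistocytes that holds for specificity at 1.4% and 1.9% but not for all measures

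*SAP*

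**What the plan says.** The SAP document is the Results chapter of the thesis. It introduces the accuracy table for deterioration with "Table-15 shows the validity of schistocytes at different cutoff values as predictor of postpartum deterioration"; the table number there is a slip, since the table that follows is Table-12. Table-12 covers schistocytes at 0.95%, 1.4% and 1.9%. Table-13 covers ALT at 230, AST at 240 and "Initial Total Bilirubin ≥ 2.95 mg/dl". The last is introduced by "Table-14 shows the validity of schistocytes as predictor of maternal mortality in included women" and has a single cut-off of 8.2%. None of the three tables prints counts or confidence intervals. The AUCs under Figures 37 to 39 all carry 95% CIs.

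Before Table-13 the text says of the three comparators that "the validity parameters were remarkably lower than the corresponding parameters of schistocytes". It does not say which schistocyte row is meant.

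The protocol sets no cut-off for predicting deterioration or death. Its only schistocyte threshold is the ICSH value for thrombotic microangiopathy (TMA). The background text describes this "with a confident threshold value of 1" per cent, and recommendation 5 applies it "when the percentage of schistocytes is above 1" per cent.

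**The concern.** The cut-off tables are what a reader would carry to the bedside or into a larger study, and they rest on the smallest numbers: 25 women who deteriorated and 3 who died. An LR+ of 60 or a sensitivity of 100% looks decisive when printed alone. If the cut-offs were also picked from the same 100 women, the values are on average too favourable. That would apply to schistocytes and to the comparators.

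The comparative sentence adds to this. It covers all accuracy measures and all three blood tests at once, with no interval for any difference, no named schistocyte cut-off, and no use of the fact that every test was read in the same women.

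**Working it through.** **Inputs.** 25 deteriorated and 75 did not (Tables 7 to 10); 3 died and 97 survived (Table-11). Sensitivities and specificities come from Tables 12-14.

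**Reproducing the tables.** TP = sensitivity x cases; TN = specificity x non-cases. All printed PPV, NPV and LR+ values then return to rounding. For example, at 1.9%: TP = 0.80 x 25 = 20 and TN = 0.987 x 75 = 74, so FP = 1, PPV = 20/21 = 95.2%, NPV = 74/79 = 93.7%, and LR+ = (20/25)/(1/75) = 60.

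**Intervals.** Proportions use Clopper-Pearson. LR+ uses the log method, SE = sqrt(1/TP - 1/25 + 1/FP - 1/75). At 1.9%, SE = sqrt(0.05 - 0.04 + 1 - 0.0133) = 0.998, and 60 x exp(±1.96 x 0.998) gives 8.5 to 425.

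| Row | TP/FN/FP/TN | Sensitivity % | Specificity % | PPV % | LR+ |
|---|---|---|---|---|---|
| Schistocytes 0.95% | 22/3/11/64 | 88 (68.8-97.5) | 85.3 (75.3-92.4) | 66.7 (48.2-82.0) | 6.0 (3.4-10.6) |
| Schistocytes 1.4% | 21/4/3/72 | 84 (63.9-95.5) | 96 (88.8-99.2) | 87.5 (67.6-97.3) | 21 (6.8-64.5) |
| Schistocytes 1.9% | 20/5/1/74 | 80 (59.3-93.2) | 98.7 (92.8-100.0) | 95.2 (76.2-99.9) | 60 (8.5-425) |
| ALT 230 | 15/10/21/54 | 60 (38.7-78.9) | 72 (60.4-81.8) | 41.7 (25.5-59.2) | 2.1 (1.3-3.5) |
| AST 240 | 15/10/12/63 | 60 (38.7-78.9) | 84 (73.7-91.4) | 55.6 (35.3-74.5) | 3.8 (2.0-6.9) |
| Bilirubin 2.95 | 17/8/14/61 | 68 (46.5-85.1) | 81.3 (70.7-89.4) | 54.8 (36.0-72.7) | 3.6 (2.1-6.3) |
| Death, 8.2% | 3/0/4/93 | 100 (29.2-100) | 95.9 (89.8-98.9) | 42.9 (9.9-81.6) | see below |

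For Table-14 the plain log method gives 24.25 (9.3-63.3). The deaths add no variance there, because 1/3 - 1/3 = 0. With 0.5 added to each cell, LR+ = (3.5/4)/(4.5/98) = 19.1 (7.2-50.5).

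**Paired comparison.** The tests were read in the same women, so the exact McNemar test applies, but the number positive on both tests is not published. I varied it over every value the margins allow. Example: 22 and 15 of 25 give discordant pairs from 7/0 (p = 0.016) to 10/3 (p = 0.092). Entries are schistocytes minus comparator in percentage points, with the possible range of p. Cut-offs are treated as fixed.

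| | 0.95% | 1.4% | 1.9% |
|---|---|---|---|
| Sensitivity v ALT, and v AST (both 15/25) | +28 (0.016-0.092) | +24 (0.031-0.18) | +20 (0.063-0.30) |
| Sensitivity v bilirubin | +20 (0.063-0.23) | +16 (0.13-0.39) | +12 (0.25-0.58) |
| Specificity v ALT | +13.3 (0.002-0.11) | +24 (at most 0.0003) | +26.7 (at most 0.00002) |
| Specificity v AST | +1.3 (1.0) | +12 (0.004-0.035) | +14.7 (0.001-0.003) |
| Specificity v bilirubin | +4 (0.25-0.69) | +14.7 (0.001-0.013) | +17.3 (0.0002-0.001) |

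**Origin of the cut-offs.** Two carry a sign of choice from the data. The 8.2% value lies just under the lowest value among the deaths, 8.3%, in "Table-11 Difference between Women who Died and Women who Survived regarding Schistocytes Percentage", which fixes sensitivity at 100%. Bilirubin is printed to one decimal in Tables 5, 6 and 9, so 2.95 is a half-step, as a mid-point between neighbouring values would be. For the others the origin is unknown.

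**The ICSH value.** The protocol estimates the percentage "after counting at least 1000 RBCs in optimal areas of the film". With exactly 1000 cells the steps are 0.1%, and at least 0.95% then means at least 1.0%, not above 1%. A row above 1% can be bounded. There are 33 women at or above 0.95% and 24 at or above 1.4%. All 3 deaths are in the upper group, so survivors ranked 68-76 of 97 lie between the two cut-offs. The survivor upper quartile of 1.1% (Table-11) falls at rank 73-74, so at least ranks 74-76 exceed 1%. Between the cut-offs are 1 case and 8 non-cases, which gives TP 21-22 and FP 5-11. Hence sensitivity is 84-88%, specificity 64/75 to 70/75 = 85.3-93.3%, PPV 21/32 to 22/27 = 65.6-81.5%, and LR+ 5.7-13.2.

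**The case against.** The strongest defence is that the denominators are printed elsewhere, so a careful reader can rebuild every count and see that 100% of 3 deaths is 3/3. The protocol calls this a pilot. Three schistocyte cut-offs are shown openly rather than one selected optimum. The supplied results start at Table-4, so a methods section may explain the cut-offs. All of this stands. It limits the point to imprecision that is recoverable but not shown, and to an origin that is unstated in the text at hand. A pilot still needs to show its uncertainty.

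Three stronger readings are tempting and not supported.

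- A reader might infer that schistocytes are no better than the liver tests. The tables do not show that: schistocytes lead on every measure in every row of Table-12. At 1.9% the lower limit for LR+ (8.5) is above the upper limits for ALT, AST and bilirubin (3.5, 6.9 and 6.3).
- A reader might infer that every cut-off was tuned to the data. Only 8.2% and 2.95 show a sign of it; ALT 230 and AST 240 are round numbers. Nor would optimism necessarily favour schistocytes. In a simulation that assumes equal-variance normal scores, 25 cases, 75 non-cases and a cut-off maximising sensitivity + specificity - 1, that index is too high by about 0.08 at AUC 0.883, 0.10 at 0.772 and 0.11 at 0.694. Those are the AUCs of schistocytes, bilirubin and AST.
- A reader might infer that the missing row above 1% hides a poor result. Its specificity, PPV and LR+ would be below those at 1.4% and 1.9%, but its sensitivity would be no lower. That is the usual trade-off. The ICSH value is a TMA threshold, the protocol words it both as 1% and as above 1%, and the 0.95% row may already equal at least 1.0%.

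**Conclusion.** The point holds as a reporting and interpretation fault that should be corrected. The arithmetic in Tables 12-14 is sound; the precision is missing. With 25 cases the sensitivity intervals are about 29 to 40 points wide, and with 3 deaths about 71.

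The broad comparative sentence needs narrowing. For specificity at 1.4% and 1.9% it is supported against all three comparators (p at most 0.035 for any pairing). For specificity at 0.95% it is not supported against AST (64 v 63 of 75) or bilirubin (p at least 0.25), and against ALT it depends on the pairing. For sensitivity, no pairing reaches p < 0.05 against bilirubin at any row, or against ALT or AST at 1.9%. Against ALT and AST at 0.95% and 1.4% it depends on the pairing. With so few cases, failing to reach 0.05 does not show equality.

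These results treat the cut-offs as fixed, make no multiplicity adjustment, and rest on counts rebuilt from rounded percentages. Whether the cut-offs are data-derived is an inference for 8.2% and 2.95 and unknown for the rest.

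**What to change.** 1. Add counts and exact 95% CIs for sensitivity, specificity, PPV and NPV to all rows of Tables 12-14, and log-method CIs for LR+ in Tables 12-13. In Table-14, omit LR+ or give the 0.5-corrected value with its interval.
2. Replace the comparative sentence before Table-13 with paired differences in sensitivity and specificity and their CIs, from patient-level data, against ALT, AST and bilirubin, naming the schistocyte cut-off compared.
3. State the selection rule for each cut-off if it is not given elsewhere. Label data-derived ones exploratory, schistocyte and comparator alike. For Tables 12-13 give bootstrap optimism-corrected values that repeat that rule in each resample; until the rule is known this cannot be done. Do not attempt it for Table-14 with 3 deaths.
4. Optionally, add a row above 1% to Table-12, labelled as the ICSH threshold for TMA and not as a rule for deterioration. Otherwise state that the 0.95% row equals at least 1.0%, if counts are in 0.1% steps.

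Item 1 needs only the counts shown here. Items 2 and 3, and the row in item 4, need a short re-analysis of data already held, with no new patients. The price is figures that look less certain, and corrected values that may be somewhat lower for every test.
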